5.2 Phase 2: Interactive Consensus Workshop and Trial Design (Months 5-9)

Having performed a survey to establish current practice and equipoise in key clinical scenarios of women presenting in preterm labour, we will convene an interactive working of approximately 40 participants with a broad range of experience and expertise. This workshop will include the co-investigator team, multidisciplinary experts, clinicians, women, patient groups, and key stakeholders to determine what kind of trial/trials still need to be done, and what groups of women should be included to address outstanding research questions. The aim is to use Delphi methodology to refine the clinical uncertainties, to inform the design of a clinical trial.

A two-round Delphi consensus methodology will be used to reduce the survey list of clinical uncertainties into a short-list, prioritising those clinical scenarios which are both uncertain and important. The Delphi methodology enables all stakeholders to participate in a consensus process which assesses the extent of agreement (about priorities) and then resolves disagreement (Sinha, Smyth et al. 2011). All stakeholder groups including parents, healthcare professionals, researchers and healthcare regulators will be invited to participate.

Two rounds of the Delphi process will take place using a web-based survey application that has been developed by the University of Liverpool (DelphiManager) and adopted by the Comet Initiative (comet-initiative.org/delphimanager). Our survey will be hosted within an online portal and infrastructure designed by the University of Liverpool. Before entering the exercise, participants will be asked to register, provide demographic details, and commit to all rounds. After this has been reviewed a unique identifier will be allocated. The unique identifier will anonymise participant responses but also provide a means to send completion reminders. Participants will also be given the option of a paper (postal) questionnaire, if they do not have access to a computer.

a) Pilot

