The Delphi questionnaire will be piloted to ensure the ease of completion by participants prior to recruitment. The Delphi survey will be piloted on the study committee and the PPI panel. This is to ensure that the outcome terminology is understood by stakeholders before allowing them to decide which outcome is important to them in the Delphi. Since those participating in the pilot are part of the study team, formal consent will not be taken.

b) Round One

Potential participants will receive an e-mail linking to the web-based questionnaire embedded within the study's website. (We will send a postal questionnaire to those who state that they do not have regular access to a computer). Initial questions will include the option to add additional scenarios for use in round two before proceeding to scoring. Even though it is likely these additional proposed scenarios would have been previously dropped from the longlist, this failsafe step will be able to identify any scenarios that may merit reconsideration.

Participants will score each clinical scenario listed using the Likert type scale, using a composite of "importance" and "clinical uncertainty" about the scenario in question. The scores will be summarised graphically using the DelphiManager.

c) Round two

The scenarios will be carried forward to round two. An anonymous summary of the responses will be fed back to participants according to each stakeholder group. Participants will be asked to re-score their preference to reach consensus. Any outcomes not deemed important by the pre-specified scale will be dropped.

d) Final Consensus meeting

An interactive consensus meeting will take place following the completion of the Delphi process to validate the final set of scenarios. The meeting will present scenarios retained and dropped by the Delphi process and discuss any scenarios in Delphi round 2 where "no consensus" was found. Only those stakeholders who completed both rounds of the Delphi study will be invited to participate. It is anticipated that 2-3 key participants from each stakeholder group will participate.

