6 STUDY POPULATION

6.1 NUMBER OF PARTICIPANTS

We plan to recruit in each phase:

Phase 1: Survey. We hope to survey around 200 clinicians on current opinion and practice and 200 members of the public

Phase 2: Consensus workshops and Delphi process will involve clinicians (including members of the co-investigator team), and other key stakeholders including women and their partners. We aim to ensure that 20-40 participants complete at least two rounds of the Delphi consensus exercise.

Phase 3: **Qualitative** interviews and focus groups: We will conduct interviews with clinicians (n=25) and focus groups with women (n=30-60) (i.e. 6-8 focus groups involving 5-8 women per group).

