13 STATISTICS AND DATA ANALYSIS

13.1 SAMPLE SIZE CALCULATION

Our planned sample sizes are as follows:

- Clinician survey, n= 200
- Public survey, n= 200
- Interactive working group, n=40
- Focus groups with women, n=30-60
- Interviews with clinicians, n=25

There are no generally accepted guidelines for the optimal size to achieve a consensus in Delphi studies [44] however it is most important to obtain a sample with a broad range of experience and expertise. Approximately 40 participants will be recruited.

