13.2 PROPOSED ANALYSES

The survey data will be used to determine current practice and public opinion. We will use a Likert scale 1-5 and analyse with appropriate non-parametric and/or parametric tests. Where more than 85% of individuals responding to the surveys agree on an answer to a clinical scenario, we will designate the scenario as having good agreement, and being accepted clinical practice. Where less than 50% agree on an answer, we will assume that there is significant uncertainty. Where 50-70% agree, we will designate the scenario as having moderate uncertainty. Where 70-85% agree, we will designate the scenario as having some uncertainty.

Data analysis for the Consensus. Delphi process will involve graphical summation of the scores indicating the whole groups' and individual participant groups' responses using the Delphi Manager. Participants will be asked to score each scenario using the Grading of Recommendations Assessment Development and Evaluations (GRADE) scale for Delphi processes (accessed online). Participants will be asked for example: 'How important is to include the following scenarios in a randomised trial of mode of delivery (caesarean/vaginal) for a preterm baby?' A pre-specified scale and criteria (Williamson, Altman et al. 2012)will be used for dropping and retaining items in the long-list created from the survey: scenarios with >70% participants scoring 7-9 and <30% scoring 1-3 would be included in subsequent rounds.

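### The Delphi criterion in section 13.2 has a clause that can never exclude a scenario, does not separate dropped from no-consensus scenarios, and conflicts with section 5.2 on when dropping happens

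*Protocol*

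**What the plan says.** Section 5.2 fixes the number of rounds and the purpose: "A two-round Delphi consensus methodology will be used to reduce the survey list of clinical uncertainties into a short-list". In round one, participants may add scenarios for use in round two and then score the list. For round two, section 5.2 c) says "The scenarios will be carried forward to round two", with no score condition attached. Summaries are then fed back by stakeholder group, participants re-score, and only after that comes "Any outcomes not deemed important by the pre-specified scale will be dropped" (read here as referring to scenarios). Under 5.2 d) the final meeting is shown what was retained and what was dropped, and is also to "discuss any scenarios in Delphi round 2 where 'no consensus' was found". The shortlist is finalised at that meeting.

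Section 13.2 supplies the only numerical criterion. It refers to a pre-specified scale and criteria from a cited paper that "will be used for dropping and retaining items in the long-list created from the survey", and then states one condition: "scenarios with >70% participants scoring 7-9 and <30% scoring 1-3 would be included in subsequent rounds".

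On numbers, section 6.1 says "We aim to ensure that 20-40 participants complete at least two rounds of the Delphi consensus exercise" and section 13.1 says "Approximately 40 participants will be recruited".

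**The concern.** Three things do not fit together.

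1. The criterion is written as two tests, high support and limited opposition, but the second follows from the first.
2. The criterion is said to serve both dropping and retaining, yet only an inclusion condition is printed. The meeting relies on a third class that has no boundary.
3. The condition governs entry to later rounds, which places the cut before feedback. Section 5.2 places it after feedback and re-scoring.

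The Delphi output feeds the shortlist, the shortlist feeds the mock trial protocol, and that protocol is what clinicians and women are asked about in Phase 3. If the criterion is unclear, someone has to decide with the scores in view which scenarios count as dropped and which are reopened. If the round-one filter is applied, scenarios can be lost before the step that section 5.2 relies on to resolve disagreement.

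**Working it through.** **Inputs.** Thresholds of 70% and 30%: section 13.2. Two rounds: section 5.2. Completers, 20 to 40: section 6.1. There is no stated sample-size or power figure for the Delphi to reproduce.

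**Step 1: does the second clause do anything?** Let H, M and L be the shares scoring 7-9, 4-6 and 1-3, taken over the same participants.

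- H + M + L ≤ 1, so L ≤ 1 − H.
- If H > 0.70, then L < 0.30. The second clause is always met.

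Exact enumeration for n = 1 to 200 gives 126,690 combinations of high and low counts with H > 0.70. None fails the second clause. The limits at three panel sizes are:

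| n | Fewest high scores with H > 70% | Most low scores possible | Possible score patterns | Retained with both clauses | Retained with first clause only |
|---|---|---|---|---|---|
| 20 | 15 (75.0%) | 5 (25.0%) | 231 | 21 | 21 |
| 30 | 22 (73.3%) | 8 (26.7%) | 496 | 45 | 45 |
| 40 | 29 (72.5%) | 11 (27.5%) | 861 | 78 | 78 |

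The last two columns agree, so the two-part rule and the single threshold keep the same scenarios. Reading the first clause as 70% or more changes little: the second clause would then exclude one pattern at each n (14 high and 6 low at n = 20; 28 high and 12 low at n = 40). The text, however, says more than 70%.

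A ceiling on low scores, written as *fewer than c*, excludes something only if c is at or below the largest possible low share: 27.5% at n = 40 and 25% at n = 20. Of the 78 retained patterns at n = 40, a ceiling of 25% would exclude 3, 20% would exclude 10 and 15% would exclude 21. These ceilings are illustrations and do not come from the protocol.

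**Step 2: how many classes does the criterion give?** It sorts scenarios into those that meet the condition and those that do not. At n = 40 the second group holds 861 − 78 = 783 patterns. It includes 26 high, 14 middle and 0 low (65% high, no opposition) and also 0 high, 0 middle and 40 low. Section 5.2 d) treats dropped and no-consensus scenarios differently, but nothing printed says which of these two is which.

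**Step 3: when is the criterion applied?**

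| | Section 13.2 | Section 5.2 c) |
|---|---|---|
| Entry to round two | Subject to the score condition | Carried forward, no condition stated |
| When scenarios are dropped | By non-inclusion in later rounds | After feedback and re-scoring |

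With two rounds, the only later round after round one is round two. The 13.2 condition is therefore a filter between the rounds. Scenarios added during round one for use in round two may have no full set of round-one scores to which such a filter could be applied.

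**Illustration of an early cut.** Suppose the filter acts at round one and each participant independently scores 7-9 with probability p. The value of p is an assumption; the protocol gives none. A scenario is cut if at most 28 of 40, or at most 14 of 20, score high.

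| Assumed p | P(cut), n = 40 | P(cut), n = 20 |
|---|---|---|
| 0.75 | 0.285 | 0.383 |
| 0.85 | 0.012 | 0.067 |

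The result depends heavily on how close p lies to the cut-off.

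**The case against.** The strongest reply is that little is broken. The rule can be run as a single threshold, and a clause that never binds misclassifies nothing. This stands: a reader might infer that the Delphi cannot be carried out as written, and the text does not support that.

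Next, section 13.2 does not say that every scenario failing the condition is dropped. Section 5.2 plainly intends three outcomes, and the cited criteria may supply the missing boundaries, which cannot be checked here. This also stands. A reader might infer that the protocol fixes a binary rule and so rules out a no-consensus result, but that goes beyond the text. What remains is that the one printed condition cannot tell dropped from no consensus.

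Third, the meeting is shown the dropped scenarios and finalises the shortlist, so the criterion alone does not choose the trial's scenarios. That is a real safeguard and it lowers the stakes. It does not say which scenarios are open for discussion.

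Fourth, section 5.2 c) does not say that *all* scenarios go forward, and section 6.1 allows for at least two rounds, so the clash over timing could be read away. But 5.2 fixes two rounds, states no filter, and puts dropping after re-scoring. The plain reading is a conflict.

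Finally, retaining 29 high and 11 low, or not retaining 26 high and 14 middle, may reflect a preference about thresholds, and any cut-off has sampling error near it. That is fair. Neither example shows that 70% is the wrong threshold, and the early-cut probabilities are illustrations, not a measure of the defect.

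The clause could bind if its two percentages used different groups, such as all participants for one and each stakeholder group for the other. Section 13.2 mentions group-level results only for graphical summary.

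**Conclusion.** The point holds in three limited parts.

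- The low-score clause is inert at every panel size, given one common denominator. This is a certainty and does not depend on any assumed response rate.
- The printed criterion does not provide the three-way split that the final meeting uses. At n = 40 it leaves 783 of 861 possible patterns undivided. These are counts of patterns, not probabilities.
- Sections 13.2 and 5.2 c) disagree, on their plain reading, about whether scenarios can be lost after round one.

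The matter deserves correction before round one opens, because the protocol itself fixes the rule and contradicts itself on its use. It is not critical: the process can still run, and the shortlist is settled by discussion at a meeting that sees the dropped scenarios too.

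**What to change.** In section 13.2:

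1. State that all round-one scenarios, including those added by participants, go to round two, and that the criteria apply only to round-two scores. This brings 13.2 into line with 5.2 c).
2. Define three classes. Consensus in: more than 70% score 7-9. Consensus out: more than 70% score 1-3. No consensus: everything else, for discussion at the final meeting.
3. Either delete the 30% clause or replace it with a lower ceiling that the team chooses before round one. To have any effect it must be at or below 27.5% with 40 participants or 25% with 20; 15% is only an illustration.

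The change is one of wording, but it has a cost in workload. More scenarios are re-scored in round two, and possibly many more reach the meeting: under these three classes at n = 40, 78 patterns are in, 78 are out and 861 − 78 − 78 = 705 are no consensus. How many real scenarios that means depends on the scores, which the pattern count does not predict. The meeting, planned with two or three key participants per stakeholder group, should be prepared for a longer agenda.

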14 ADVERSE EVENTS

We do not anticipate any adverse outcomes from this study. However, we recognise that discussion of method of delivery might be upsetting for women and families (and indeed staff) who have experienced adverse events. Focus groups will be conducted by experienced researchers, who will be alert for any signs of distress, and who can refer individuals for further support of advice if required. The extended research team will be available for advice and support, and we are fortunate to have charities Bliss and TOMMY's as partners – these charities regularly provide information and support to women and partners who have experienced adverse events and have helplines that can support parents (and staff if necessary). We will signpost participants to these helplines and to other relevant health care professionals as relevant and necessary.

15 OVERSIGHT ARRANGEMENTS

15.1 INSPECTION OF RECORDS

Investigators and institutions involved in the study will permit trial related monitoring and audits on behalf of the sponsor, REC review, and regulatory inspection(s). In the event of audit or monitoring, the Investigator agrees to allow the representatives of the sponsor direct access to all study records and source documentation. In the event of regulatory inspection, the Investigator agrees to allow inspectors direct access to all study records and source documentation.

15.2 RISK ASSESSMENT

A study specific risk assessment will be performed by representatives of the co-sponsors, ACCORD monitors and the QA group, in accordance with ACCORD governance and sponsorship SOPs.

15.3 STUDY MONITORING AND AUDIT

The ACCORD Sponsor Representative will assess the study to determine if an independent risk assessment is required. If required, the independent risk assessment will be carried out by the ACCORD Quality Assurance Group to determine if an audit should be performed before/during/after the study and, if so, at what frequency.

Risk assessment, if required, will determine if audit by the ACCORD QA group is required. Should audit be required, details will be captured in an audit plan. Audit of Investigator sites, study management activities and study collaborative units, facilities and 3rd parties may be performed.

16 GOOD CLINICAL PRACTICE

16.1 ETHICAL CONDUCT

The study will be conducted in accordance with the principles of Good Clinical Practice (GCP). Before the study can commence, all required approvals will be obtained and any conditions of approvals will be met. Investigators are responsible for the overall conduct of the study and compliance with the protocol and any protocol amendments in accordance with the principles of GCP. Responsibilities may be delegated to an appropriate member of study site staff.

16.2.1 Informed Consent

The Investigator or delegate is responsible for ensuring informed consent is obtained before any protocol specific procedures are carried out. The decision of a participant to participate in clinical research is voluntary and should be based on a clear understanding of what is involve.

We are assuming that those who respond to the survey consent to participate in it, but we will be clear with the respondents about how we will use the information.

Participants must receive adequate oral and written information – appropriate Participant Information and Informed Consent Forms will be provided, where practical. The oral explanation to the participant will be performed by the Investigator or qualified delegated person, and must cover all the elements specified in the Participant Information Sheet and Consent Form.

The participant must be given every opportunity to clarify any points they do not understand and, if necessary, ask for more information. The participant must be given sufficient time to consider the information provided. It should be emphasized that the participant may withdraw their consent to participate at any time without loss of benefits to which they otherwise would be entitled.

The participant will be informed and agree to their medical records being inspected by regulatory authorities and representatives of the sponsor(s).

The Investigator or delegated member of the trial team and the participant will sign and date the Informed Consent Form(s) to confirm that consent has been obtained. The participant will receive a copy of this document and a copy filed in the Investigator Site File (ISF) and participant's medical notes (if applicable).

16.2.2 Study Staff

The Investigator must be familiar with the protocol and the study requirements. It is the Investigator's responsibility to ensure that all staff assisting with the study are adequately informed about the protocol and their trial related duties.

16.2.3 Data Recording

16.2.4 Investigator Documentation

The Lead investigator for each aspect of the study will ensure that the required documentation is retained for the required period. All data will be archived centrally at the University of Edinburgh for the required period of time.

16.2.5 GCP Training

For this study all researchers are encouraged to undertake Good Clinical Practice (GCP) training, however, it is not a mandatory requirement. GCP training status for all investigators will be indicated in their respective CVs.

16.2.6 Confidentiality

All forms, reports, and other records must be identified in a manner designed to maintain participant confidentiality. All records must be kept in a secure storage area with limited access. Clinical information will not be released without the written permission of the participant. The Investigator and study staff involved with this study may not disclose or use for any purpose other than performance of the study, any data, record, or other unpublished, confidential information disclosed to those individuals for the purpose of the study. Prior written agreement from the sponsor or its designee must be obtained for the disclosure of any said confidential information to other parties.

16.2.7 Data Protection

All Investigators and study site staff involved with this study must comply with the requirements of the General Data Protection Regulations (GDPR) 2018 with regard to the collection, storage, processing and disclosure of personal information and will uphold the Act's core principles. Access to collated participant data will be restricted to individuals from the research team treating the participants, representatives of the sponsor(s) and representatives of regulatory authorities.

Computers used to collate the data will have limited access measures via user names and passwords.

Published results will not contain any personal data that could allow identification of individual participants. Anonymized data will be shared (if requested) with other researchers within the European Union as per the funders data sharing policy.

17 STUDY CONDUCT RESPONSIBILITIES

17.1 TEAM RESPONSIBILITIES

[name] will have overall management of the project (and will Chief Investigator), assisted by [name], who will provide study management support.

Phase 1: The clinician and public surveys will be led by [name].

Phase 2: The Delphi consensus exercise to finalise the research questions, will be led by [name]. [name] and [name] will design the trial.

Phase 3: The qualitative research with women and clinicians in phase 3 will be led by [name] and [name]. [name] (Tommy's) and [name] (Bliss) will help with identifying women from Tommy's and Bliss respectively to participate in focus groups. [name], [name], [name] and [name] will help identify women and health professionals to participate from their NHS sites.

Communication will be achieved through regular teleconferences (anticipated monthly), face to face meetings (likely half yearly) and other email etc. as required. A Trial Steering Committee (but not a data monitoring committee) will be set up in line with funder recommendations.

